**Cluster Randomized Trial of a School-Based Program to Prevent Teen Dating Violence**  
**NCT02909673**  
**7/21/20**

**Cluster Randomized Trial of a School-Based Program to Prevent Teen Dating Violence**  
**[name]. – Principal Investigator**

**Study Protocol**

**Purpose of Research:** The purpose of this NIH funded study is to evaluate the new and enhanced middle school version of *Fourth R*, a healthy relationships and prevention program previously shown to be effective in reducing risky behaviors and improving relationships among high school students.

**Specific Aims:** The primary aim is to determine whether *Fourth R* reduces students' teen dating violence (TDV), as indexed by less perpetration and victimization of physical, sexual, and psychological TDV, relative to students in control schools. The secondary aims are to determine whether *Fourth R*, relative to control, (1) improves students' emotional well-being, and increases their acquisition and use of healthy relationship skills, as indexed by improved problem-solving, communication, and conflict resolution skills and (2) ameliorates the modifiable cognitive and behavioral correlates associated with the perpetration and victimization of TDV, as indexed by fewer attitudes justifying dating violence, decreased substance use, decreased risky sexual behavior, decreased fighting and bullying, increased school connectedness, improved academic performance, and decreased psychological symptoms. Pre-specified differences by gender and ethnicity will be examined, as well as the acquisition and utilization of various program components.

**Research Design:** This five year study is a school-based cluster randomized trial (experimental design) of the middle school version of *Fourth R*, where students receiving the curriculum will be compared to students receiving usual health classes. Outcomes will be assessed at baseline and at 12, 24, and 36 months post intervention.

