**Sampling Design and Rationale:** We will recruit 24 middle schools in the Houston area for the study. A cluster-randomized trial will be used to assign the 24 participating middle schools (i.e., clusters) to the intervention (n=12) or control (n=12 as usual health classes) condition. Students (N=3,000) in these schools will be the unit of analysis and will be studied prospectively to determine the program's impact by comparing intervention students with control students. Outcomes will be assessed at baseline (when students are in 7th grade), and at 12-, 24-, and 36-months post-intervention, when students are in 8th, 9th, and 10th grade, respectively. To minimize school disruption, only the 1-year follow-up survey will be conducted in schools; the 2- and 3-year follow-up will be conducted via a web-based survey. The primary hypothesis is that intervention students will have significantly lower prevalence of physical, psychological, and sexual TDV perpetration and victimization than control students. The secondary hypothesis is that intervention students will have better healthy relationship skills (problem-solving, communication, conflict resolution), higher levels of school connectedness, better decision-making with respect to substance use and risky sexual behavior, better academic performance, and better mental health and well-being than control students.

**Recruitment:** The research team will recruit in 7th grade health classes at participating schools. A multi-method approach will be used for recruitment and to obtain parental permission. First, with district and school approval, research staff will include parental consent forms in the beginning-of-the-semester packets that are sent home with all students and parents will be asked to review, sign, and return. All consent materials will be provided in English and Spanish. Please see enclosed letter to parents, parent permission form, and student assent form. Second, research staff will actively follow up with "non-respondents" via phone and email. Third, to reach students who do not return a parental permission form, research staff will describe the purpose, design, and enrollment criteria to 7th graders

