Implementing teachers will be asked to complete curriculum monitoring (fidelity) and attendance sheets. Research staff will follow up with teachers to ensure these are completed. The site coordinator at each school will collect forms from teachers. With district and principal approval, research staff will attend 10% of the lessons delivered by each facilitator. Standardized checklists used by *Fourth R* staff that list main points and activities of each lesson will be utilized. Other observations will include percentage of time teachers use interactive instructional techniques, student behavior, deviations from the curriculum, and class size.

**Data Collection Procedures:** Students will be asked to complete paper/pencil surveys or web-based surveys hosted on a secure server (paper/pencil surveys will be completed when computers are unavailable). Prior to participating in the baseline survey, students will receive information about the study, what will be asked of them over the study period, and how their confidentiality will be protected. If they choose to participate in the survey, students will complete an assent form (parental permission will have already been obtained). Baseline and the 1-year follow-up will be conducted in the schools using paper and pencil surveys or school computers for web-based surveys during regular class time (paper/pencil surveys will be completed when computers are unavailable). We will employ the services of the Survey Research Division (SRD) at the University of Washington (UW) to assist with participant retention and the follow-up assessments. A majority of students will complete the 1-year follow-up survey in school, and any remaining students will complete the survey outside of the school setting via a mixed-mode approach (web, telephone, and paper surveys). Because participants will have transitioned from middle schools to high schools, the 2- and 3-year follow-ups will be done outside of the school setting via the mixed-mode approach. Students will receive a \$5 gift card for completing the baseline assessment, \$10 for completing the 1-year follow-up, and \$20 for the 2-year and 3-year follow-ups.

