**Data Analysis:** The primary objective of the data analysis is to evaluate the effectiveness of the *Fourth R* intervention in reducing TDV perpetration and victimization among a 7th–10th-grade population. Data analysis will be conducted in 5 phases: (1) preliminary analysis, (2) confirmatory analysis, (3) exploratory analysis, (4) attrition analysis, and (5) cost-effectiveness analysis. Preliminary analysis will be conducted using baseline data to produce a profile of the sample with regard to demographics and baseline outcome characteristics. This analysis will consist of descriptive statistics, such as frequencies, means, cross tabulations, and graphical representations of the data. The results from this analysis will provide information on imbalances between study groups that should be accounted for in the confirmatory analysis. Confirmatory analysis will be conducted to test the proposed hypotheses, which have been stated a priori, within the context of the study design. Linear and generalized linear regression models will be used to test for intervention effects while controlling for baseline differences through the use of covariates. The study design is composed of data collected on students within schools. Data from students within the same school are anticipated to be correlated to varying degrees.

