Two-level multilevel models will be used to assess the impact of the intervention in the presence of this correlation where level-1 is the student measurement and level-2 is the school unit. Application of traditional regression estimation techniques, which assume independence between observations, to correlated data can lead to an underestimation of the standard error, resulting in an increased probability of Type I error. Results from this analysis will be used to answer the primary research questions. Analyses will also be conducted to assess the impact of the intervention on the secondary outcome measures and to investigate the nature of their relationship to changes in TDV behavior. Exploratory analysis will be conducted after all primary and secondary research questions have been addressed. The purpose of this analysis is to identify relationships and patterns in the data that may not have been anticipated in the onset of the study. All results from this analysis will be labeled as exploratory in nature and will be used for the purpose of yielding evidence that is suggestive of hypotheses to be considered in subsequent studies. Attrition analyses will be conducted at all follow-up time points to assess patterns of missingness. These patterns will be quantified and documented as to their potential impact on the generalizability of findings. In the event that these analyses reveal nonrandom missing patterns that may impact program generalizability, imputation techniques will be employed. Additionally, will measure cost-effectiveness of the program relative to standard instruction. Specifically, we will examine the (1) cost-effectiveness of Fourth R in decreasing the number of students who are victims or perpetrators of TDV, (2) cost-benefit of Fourth R in preventing cases of injury due to TDV, and (3) cost-utility of Fourth R in increasing the quality-adjusted life years (QUALYs) saved by estimating the cost per QUALY saved. Finally, we will conduct a cost analysis of Fourth R from the school-district perspective to inform administrators and decision-makers about the costs and benefits that a school is likely to incur by adopting Fourth R. In this analysis, only school-related costs and benefits will be included. Program costs will include materials paid for by the school and personnel time costs. Benefits will include school costs averted because of the program.

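### Does a two-level model with three follow-ups per student and only 24 schools make the trial's tests too liberal?

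*Combined protocol and SAP*

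**What the plan says.** The Research Design paragraph sets the schedule: "Outcomes will be assessed at baseline and at 12, 24, and 36 months post intervention". Under Measures, the full set is repeated at every wave. Sampling Design and Rationale will "assign the 24 participating middle schools (i.e., clusters) to the intervention (n=12) or control", and the same paragraph makes the 3,000 students the unit of analysis. The primary hypothesis there is that "intervention students will have significantly lower prevalence of physical, psychological, and sexual TDV perpetration and victimization than control students".

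Data Analysis describes the data structure in one sentence, "The study design is composed of data collected on students within schools", and tests intervention effects by linear and generalized linear regression while "controlling for baseline differences through the use of covariates". The levels are given as "level-1 is the student measurement and level-2 is the school unit". The reason offered is that ignoring within-school correlation understates standard errors and raises Type I error.

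Specific Aims adds that "Pre-specified differences by gender and ethnicity will be examined", but Data Analysis gives no model or test for these differences. The section also contains no time term, student effect, residual covariance, primary time point or degrees-of-freedom method, and it does not mention pooling the follow-ups.

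**The concern.** Level 1 is called the student measurement, not the student. Read literally, that could mean one row per student per wave nested directly in school, with nothing to link a student's own answers. Those answers are correlated, so treating them as independent within school understates the standard error of any contrast estimated within schools. An arm-by-gender or arm-by-ethnicity interaction is such a contrast. A chance subgroup difference could then be reported as a planned finding, and the protection against Type I error that the section claims for its model would be missing there.

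The second worry concerns the arm effect. It is a comparison of 12 schools with 12, and a large-sample z test on so few clusters rejects somewhat too often. Schooling also changes during the study: "Because participants will have transitioned from middle schools to high schools, the 2- and 3-year follow-ups will be done outside of the school setting". A reader may therefore wonder which school defines level 2 in the later waves.

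**Working it through.** **Inputs.** From the documents: 24 schools (12 per arm), 3,000 students (3000/24 = 125 per school), three follow-ups, two model levels, baseline covariates. Not in the documents, so assumed: two-sided 5% level, within-student correlation *r* of 0.2 to 0.7, school intraclass correlation of 0.01 to 0.03. The plan gives no error rate or sample-size calculation that could be reproduced first.

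**1. Separate model per wave.** There is one record per student, so student within school is the complete structure. In null simulations (random-intercept linear model, REML, 24 schools of 75 to 175 students, 4,000 replicates per scenario) the moderator-by-arm test rejected in 4.7% to 5.6% of trials. Under this reading there is no subgroup problem.

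**2. Waves stacked, no student level, arm-by-gender test.** With *m* waves the variance is understated by 1 + (*m* − 1)*r*, so the true level is 2[1 − Φ(1.96/√(1 + (*m* − 1)*r*))]. If the baseline value of the outcome is a covariate and all waves are equally correlated, the remaining correlation is (*r* − *r*²)/(1 − *r*²) = *r*/(1 + *r*), which is 0.167, 0.231, 0.333 and 0.412 for the four values below.

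| Case | r = 0.2 | 0.3 | 0.5 | 0.7 |
|---|---|---|---|---|
| 3 waves, unadjusted | 9.8% | 12.1% | 16.6% | 20.6% |
| 3 waves, baseline-adjusted | 9.0% | 10.5% | 12.9% | 14.7% |
| 2 waves, unadjusted | 7.4% | 8.6% | 11.0% | 13.3% |
| 2 waves, baseline-adjusted | 7.0% | 7.7% | 9.0% | 9.9% |

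Worked example, last row, *r* = 0.5: √(1 + 0.333) = 1.155; 1.96/1.155 = 1.697; two-sided tail 9.0%.

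Simulation agrees with the top-row formula. At *r* = 0.4 the formula gives 14.4%; simulation gave 13.1% and 14.9% for gender at the two intraclass correlations, and 14.2% for an ethnicity-like moderator whose share varies by school. With 75% response per wave the figure fell to 11.9%. A binary outcome at 20% prevalence with latent correlation 0.5, analysed on the linear scale, gave 12.1%.

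The last row is nearest to the plan, which adjusts for baseline covariates and prepares for non-response. Two waves per student is itself an assumption. Relative to 5%, that row is 7.0/5 = 1.4 to 9.9/5 = 2.0 times nominal.

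**3. Arm main effect.** Stacking does no harm here, because the school random intercept absorbs the student-level correlation when school means are compared. In the gender scenarios, simulated levels with a z test were 6.1% to 6.5% stacked and 5.5% to 6.6% one wave at a time. What remains is the small number of schools: with 24 − 2 = 22 degrees of freedom, P(|t₂₂| > 1.96) = 6.3%. If the variance were estimated by maximum likelihood (22/24 of the REML value), the formula gives 7.4%. On 22 degrees of freedom the critical value is 2.074, intervals widen by 2.074/1.960 = 1.058, or about 6%, and simulated levels were 4.3% to 5.4%.

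**The case for a change.** The strongest reply is that the ambiguity is real and cheap to remove. The level is named as the measurement, the section's stated objective spans 7th to 10th grade, and nothing rules out a pooled fit. The gender and ethnicity differences are called pre-specified, so an inflated test would carry more weight than an exploratory one. Any positive within-student correlation inflates it, whatever the exact value. And a z test of the primary contrast exceeds 5% however the waves enter.

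Much of this stands as description. The plan is silent on both points, the formulas are right, and one sentence would settle the matter.

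It does not show that a stated rule gives a wrong answer. The subgroup harm needs two steps that the plan does not take: stacking the waves without a student term, and testing interactions in that model. Against the first step, students are the unit of analysis, the data are described as students within schools, and exactly two levels are specified. The second step has no text behind it beyond the statement that differences will be examined. The largest figures also require complete follow-up, no baseline adjustment and a correlation of 0.7 together. As to the z test, the plan does not name one; 6.3% is the result of a choice that has not been made.

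**Conclusion.** The plan leaves two details open: how the follow-ups enter, and which reference distribution serves the arm effect. Neither is an error in what is written.

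On the more natural reading, one wave per model with the student as the unit, the two-level structure is adequate and subgroup tests keep about 5%. That reading gives three results per outcome with no primary time point named, which is a separate matter from the number of levels. An analyst who chose to combine waves would ordinarily add a student term, since the section already explains why correlated observations need one. Keeping the randomised middle school as level 2 after the move to high school follows from the design.

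If both unstated steps were taken, the interaction tests would run at roughly 1.4 to 2 times nominal with two waves and baseline adjustment, and higher with complete unadjusted waves. These figures rest on assumed correlations of 0.2 to 0.7 and the linear formula. The primary arm test is unaffected by stacking. Its possible excess is 6.3 − 5 = 1.3 percentage points under REML and exists only if a z test is used; a t reference on about 22 degrees of freedom removes it for about 6% wider intervals. Recording both choices before analysis would be good practice, but the plan does not have to change.

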data collection) that if a student becomes upset, they should offer them the option of discontinuing the survey without penalty (i.e., still receiving gift card) or continuing at a later time. Furthermore, the tailored survey administration limits student exposure to potentially sensitive items: students without a history of dating are not exposed to TDV questions; similarly, students who have not engaged in sexual behavior are not exposed to more-detailed questions about number of sexual partners or condom use. All students will also be instructed that they may skip any item that makes them feel uncomfortable. In the event of any emotional distress, research staff will remain with the student until he or she is no longer distressed. [name] will be available at all times to provide immediate supervision or to counsel students. Students who wish to pursue additional therapy will be given a referral list specifically tailored to his or her request. We will have prepared referral lists for TDV perpetration and victimization, as well as for other psychological problems. At the end of each assessment, all students will be offered a list of referrals and a teen safety plan designed specifically for adolescents in violent relationships. Of note, we have established connections with local organizations that will be available to provide counseling to participants if needed. We will not be asking about suicide as part of the program, so it is unlikely that we will have to deal with this issue. However, anyone having direct involvement with the students will be fully trained by [name] in procedures for assessing and intervening in cases where suicidal ideation is expressed. Research staff will be instructed to immediately contact [name] and the project director if suicidal ideation is expressed. Appropriate clinical action will be taken in these circumstances, including hospitalization and/or referral to another level of clinical care.

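### Does the survey's skip logic leave the risky-sexual-behavior outcome without a usable denominator?

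*Combined protocol and SAP*

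**What the plan says.** Protection against Risk describes two parallel skips. For dating violence, "students without a history of dating are not exposed to TDV questions"; for sexual behavior, "students who have not engaged in sexual behavior are not exposed to more-detailed questions about number of sexual partners or condom use". The same section adds: "All students will also be instructed that they may skip any item that makes them feel uncomfortable". A blank can therefore be a skip by design or a refusal.

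Both skips touch outcomes. TDV is primary; Sampling Design and Rationale states: "The primary hypothesis is that intervention students will have significantly lower prevalence of physical, psychological, and sexual TDV perpetration and victimization than control students". Sexual risk is secondary. Specific Aims lists "fewer attitudes justifying dating violence, decreased substance use, decreased risky sexual behavior", and the secondary hypothesis in Sampling Design and Rationale speaks of "better decision-making with respect to substance use and risky sexual behavior".

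Data Analysis specifies two-level models with students within schools. On secondary outcomes it says "Analyses will also be conducted to assess the impact of the intervention on the secondary outcome measures", without items, scores or denominators. Its cost-effectiveness part refers to "decreasing the number of students who are victims or perpetrators of TDV". It allows imputation if attrition analyses find nonrandom missingness. Measures says a draft survey is enclosed; it is not among the documents reviewed.

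**The concern.** Condom use has no case or non-case value for a student who has not had sex. Condom use among sexually active students and unprotected sex among all students both fit the text, and they can disagree. Having had sex by 12, 24 or 36 months is observed after randomization. If the program changed who is active, the active students in the two arms would no longer be the randomized groups, and any benefit from fewer students having sex would not show. With no rule written down, the choice could be made after the results are seen.

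The same silence covers the primary outcome, because dating status is also observed after randomization. Finally, if skips by design were treated as ordinary missing values, imputation could assign answers to students for whom the question has no meaning.

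**Working it through.** **Plan's own figures.** The documents give no event rates, ICC, alpha or power, so there is no stated result to reproduce. They do give 24 schools (12 per arm) and 3,000 students: 3,000/24 = 125 per school and 1,500 per arm. Every rate and ICC below is an assumption.

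**Sexual risk.** Let s_c and s_i be the shares who have had sex in control and intervention, c condom use among those active in either arm, and d condom use among students active only under control.

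- Condom users per student: control s_i·c + (s_c − s_i)·d; intervention s_i·c.
- Active-only condom use = users / share active.
- All-student unprotected sex = share active − users.

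Take s_c = 0.20, s_i = 0.16, c = 0.60, with no effect on condom use itself.

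| d | Active-only condom use, control vs intervention | All-student unprotected sex, control vs intervention | RR |
|---|---|---|---|
| 0.60 | 60% vs 60% | 8.0% vs 6.4% | 0.80 |
| 0.80 | 64% vs 60% | 7.2% vs 6.4% | 0.89 |
| 0.40 | 56% vs 60% | 8.8% vs 6.4% | 0.73 |

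For d = 0.80, control users are 0.16 × 0.60 + 0.04 × 0.80 = 0.128, and 0.128/0.20 = 64%. If s_i = s_c = 0.20, the results are 60% vs 60% and 8.0% vs 8.0%, so the codings agree. With the same 20% relative fall from a control share of 10% or 30%, the d = 0.60 case gives 4.0% vs 3.2% or 12.0% vs 9.6% unprotected sex, and the active-only percentages do not move.

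**Precision.** Variance is p(1 − p)/n times 1 + (m − 1)·ICC.

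- All students, 8.0% vs 6.4%, n = 1,500, m = 125: SE 0.0094 at ICC 0, so 0.016/0.0094 = 1.70 SE.
- An ICC of 0.01 among active students does not carry over to all students. With an equal active share in every school, the implied control-arm value is s²·ICC·p_a(1 − p_a)/[p(1 − p)] = 0.04 × 0.01 × 0.24/(0.08 × 0.92) = 0.0013. The design factor is 1 + 124 × 0.0013 = 1.16, the SE 0.0102, and the difference 1.57 SE. Using 0.01 directly would give 1.13 SE and overstate the imprecision.
- Active only, 64% vs 60%, n = 300 and 240, m = 25 and 20: SE 0.0420 (0.95 SE) at ICC 0 and 0.0463 (0.86 SE) at ICC 0.01.

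The apparent harm among active students is under 1 SE.

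**TDV.** Assume dating falls from 50% to 45%, with 10% TDV risk in those deterred and 30% in the rest. Daters only: (0.45 × 0.30 + 0.05 × 0.10)/0.50 = 28.0% vs 30.0%. All students: 14.0% vs 13.5%. The sign reverses here too, so the primary outcome is as exposed as the secondary one.

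If dating is unaffected (30% vs 24% in daters, 50% dating; t with 22 df, two-sided 0.05), daters-only power is 0.51 at ICC 0.01. All-student power is about 0.46 to 0.47 at the implied ICC of 0.25 × 0.01 × 0.21/(0.15 × 0.85) = 0.0041 (0.0043 in the intervention arm). The all-student denominator costs little.

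**The text side by side.** Sampling Design and Rationale analyzes the 3,000 students and compares intervention with control students in both hypotheses. That wording leans toward all students for TDV and for sexual risk alike; only the word prevalence is confined to the primary hypothesis. No section states a daters-only or active-only analysis. Number of partners is zero by definition for a never-active student, which leaves condom use as the one open item.

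**The case for a change.** The strongest case for a change is that a lean is not a rule. Condom use admits two codings that can differ in sign, the choice could follow the data, and a few sentences of analysis text would close it at almost no cost. The point has more force for TDV, which is primary and equally silent. The documents also leave open whether dating history and sexual activity mean ever or since the last survey. All of this is true as a description of the text.

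It shows only that detail is missing. The divergence requires the program to change who dates or has sex, or who reports it, and also requires the analyst to choose the restricted denominator against the lean of the text. For sexual risk, the documents do not say that delaying sex is intended. Condom use among active students is also a legitimate question: with d = 0.60, 60% vs 60% is its correct answer. Whether that or unprotected sex in all students should lead is a matter of judgment, and the second depends on a condom item not available here. The imputation sentence concerns patterns of attrition, so imputing skips by design would be a misuse, not something the plan directs.

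**Conclusion.** No change to the plan is needed. It gives no scoring rule for either skip, but followed as written it leads to no demonstrated wrong result. An analyst would ordinarily keep all students surveyed at a wave in the denominator, score those routed past the TDV items as having no TDV and the never-active as having zero partners, keep refusals and non-response as missing, and show dater-only or active-only results beside the share dating or active in each arm.

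The size rests wholly on assumptions. With a 20% relative fall in sexual activity, active-only condom use can move 4 points in either direction, and the 64% vs 60% case is under 1 SE. With no change in activity and no effect on condom use, the codings agree. The conclusion would be different if the plan stated a restricted denominator for TDV; it does not. The draft survey may settle the item wording and recall period.
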